10.6.3 Summaries of Baseline Characteristics and Demographics

The comparability of the treatment groups for each relevant characteristic will be assessed by the use of tables and/or graphs. No statistical hypothesis tests will be performed on these characteristics. The number and percentage of participants randomized and the primary reason for discontinuation will be displayed. Demographic variables (such as age) and baseline characteristics will be summarized by treatment either by descriptive statistics or categorical tables. The reasons for exclusion from the ITT population (if any) will be summarized.

10.7 Interim Analyses

10.7.1 Safety Interim Analyses

The eDMC will conduct regular safety monitoring. The timing of the first safety monitoring will be specified in the DMC charter. As of Amendment 05, no additional eDMCs will take place.

10.7.2 Efficacy Interim Analyses

No efficacy interim analysis is planned for this study. The study will be unblinded at the database lock for the primary analysis for ORR.

10.8 Multiplicity

The overall Type I error rate is strictly controlled at 5% (one-sided) by fixed sequence, a closed-testing procedure. The closed testing procedure will be applied to the primary hypothesis of ORR first. If the primary hypothesis is rejected at the $\alpha=5\%$ level (one-sided), then testing will continue to the key secondary hypothesis of PFS. Nominal p-value for each endpoint will be reported, where applicable, regardless of the outcome of the closed testing procedure dictated by the multiplicity strategy.

10.9 Sample Size and Power Calculations

10.9.1 Sample Size and Power for Efficacy Analyses

The study will randomize 148 participants in a 1:1 ratio into the pembrolizumab plus epacadostat and pembrolizumab plus placebo arms. ORR is a primary endpoint for the study and PFS and OS are secondary endpoints.

[Figure 3](#) summarizes power calculations for the primary hypothesis under various ORR difference assumptions.

[figure not shown]

Figure 3 Power for Primary Hypothesis under Different Effect Size Assumptions

Based on the 148 participants in the control arm and the treatment arm under comparison, the power of the ORR testing at the $\alpha=0.05$ (one-sided) is approximately 81.7% to detect a difference of 20 percentage points in ORR between an underlying 50% response rate in the control arm and a 70% response rate in the experimental arm.

With 95 PFS events, the study will have 80% power to detect a hazard ratio of 0.6 at an alpha level of 5% (1-sided).

The sample size and power calculations were performed in R (package “gsDesign”).

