Type of Control	Active Control NOTE: As of Amendment 05, active control/placebo is removed.
Trial Blinding	Double-blind NOTE: As of Amendment 05, the study is unblinded.
Estimated Duration of Trial	The study is estimated to require approximately 3 years from the time the first participant signs the informed consent until the last participant's last study-related phone call or visit.

Number of Participants:

Approximately 148 participants will be enrolled.

Treatment Groups and Duration:

Treatment Groups	
• Pembrolizumab 200 mg IV every 3 weeks (Q3W), up to 35 cycles 
NOTE: The original study design randomized participants into 2 treatment arms: pembrolizumab (open-label) plus epacadostat and pembrolizumab (open-label) plus matching placebo. As of Amendment 05, epacadostat and matching placebo are removed. All participants remaining in the study will receive pembrolizumab monotherapy as per protocol, unless they choose to discontinue from the study completely and be treated with standard of care.

Duration of Participation	
NOTE: As of Amendment 05, this section has been updated.
 
Each participant will partake in the study from the time the participant signs the informed consent form through the final contact.
 
After a screening phase of 30 days, each participant will be assigned to receive study treatment until disease progression, unacceptable AEs, intercurrent illness that prevents further administration of treatment, investigator's decision to withdraw the participant, noncompliance with study treatment or procedure requirements or administrative reasons requiring cessation of treatment, withdrawal of consent, or until the participant has received 35 administrations of pembrolizumab (approximately 2 years).
 
After the end of treatment, each participant will be followed for the occurrence of AEs and spontaneously reported pregnancy as described under Section 9.3.

Study governance considerations are outlined in Appendix 3. A list of abbreviations used in this document can be found in Appendix 1.

2. Schedule of Activities (SoA)

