3.3 Benefit/Risk Assessment

NOTE: The results of the final efficacy analysis of this study indicated that the study did not meet the pre-specified endpoint of improvement in objective response rate (ORR) for the combination of pembrolizumab plus epacadostat compared with pembrolizumab plus placebo. As of Amendment 05, epacadostat and matching placebo have been removed from the study. Therefore, the benefit:risk assessment of epacadostat is no longer applicable and has been removed.

It cannot be guaranteed that participants in clinical studies will directly benefit from treatment during participation, as clinical studies are designed to provide information about the safety and effectiveness of an investigational medicine.

[figure not shown]
Despite the substantial improvement in PFS and OS observed with pembrolizumab as compared to SOC platinum doublet chemotherapy in KEYNOTE-024, there remains a need to investigate new treatments which offer the prospect of added benefit for this patient population. Details regarding specific benefits and risks of pembrolizumab treatment for participants in this clinical study may be found in the Investigator's Brochure [IB Edition 15 2017] and Informed Consent Form (ICF).

4. Objectives/Hypotheses and Endpoints

NOTE: As of Amendment 05, epacadostat and matching placebo are removed from the treatment groups. All participants remaining on study will continue on open-label pembrolizumab monotherapy. The study will therefore stop collecting efficacy endpoints.

In all randomized participants with treatment-naïve, stage IV NSCLC, highly expressing PD-L1 (TPS \geq 50%):

Objective/Hypothesis	Endpoint
Primary	

 • To compare ORR of the combination of pembrolizumab plus epacadostat versus pembrolizumab plus placebo. • Hypothesis (H1): The combination of pembrolizumab plus epacadostat has superior ORR compared to pembrolizumab plus placebo. 	
 • ORR is defined as the proportion of participants who have a confirmed CR or PR per RECIST 1.1 based on BICR.

This study will be considered to have met its success criteria if pembrolizumab plus epacadostat is superior to pembrolizumab plus placebo in ORR.
	
Secondary	

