5.2 Number of Participants

Approximately 148 participants will be randomized into the study. The study was initially designed to recruit 588 patients. With Amendment 04, the sample size was reduced to total 148 participants randomized, inclusive of participants who were enrolled prior to Amendment 04. It was estimated that approximately 90 additional participants would be required to be randomized into the 2 treatment arms based on enrollment at the time Amendment 04 was being released. Enrollment was completed on 05-SEP-2018.

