9.9.4 Second Course Phase

NOTE: As of Amendment 05, this section is no longer applicable and has been deleted.

10. Statistical Analysis Plan

NOTE: The final analysis of the study was conducted as described below, with a data cutoff of 10-JAN-2019. Data from the final analysis showed the study did not meet the pre-specified primary endpoint of improvement in ORR for the combination of pembrolizumab plus epacadostat compared with pembrolizumab plus matching placebo. As of Amendment 05, the study will therefore stop collecting efficacy data, including central review of imaging. Thus, after study completion, only selected analyses as detailed in this section will be performed [REDACTED]

This section outlines the statistical analysis strategy and procedures for the study. If changes are made to primary and/or key secondary hypotheses or the statistical methods related to those hypotheses after the study has begun, but prior to any unblinding/final database lock, then the protocol will be amended (consistent with ICH Guideline E9). Changes to [REDACTED] other non-confirmatory analyses made after the protocol has been finalized, but prior to unblinding/final database lock, will be documented in a supplemental Statistical Analysis Plan (sSAP) and referenced in the Clinical Study Report (CSR) for the study. [REDACTED]

[REDACTED]

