Sample Size and Power	The planned sample size is approximately 148 participants with 74 participants in each arm. For the ORR test, based on all patients randomized with minimum 18 weeks of follow-up, the study has 81.7% power to detect a 20-percentage point difference in ORR for pembrolizumab+ epacadostat vs pembrolizumab+ placebo at $\alpha=5\%$ (one-sided).

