### **3.9 SAMPLE SIZE AND POWER CALCULATIONS**

#### **3.9.1 Sample Size and Power for Efficacy Analyses**

The study will randomize 148 participants in a 1:1 ratio into the pembrolizumab plus epacadostat and pembrolizumab plus placebo arms. ORR is a primary endpoint for the study and PFS and OS are secondary endpoints.

[Figure 1](#) summarizes power calculations for the primary hypothesis under various ORR difference assumptions assuming an underlying ORR of 50% in the pembrolizumab + placebo treatment group.

[figure not shown]

Figure 1 Power for Primary Hypothesis under Different Effect Size Assumptions

Based on the 148 participants in the control arm and the treatment arm under comparison, the power of the ORR testing at the  $\alpha=0.05$  (one-sided) is approximately 80.4% to detect a difference of 20 percentage points in ORR between an underlying 50% response rate in the control arm and a 70% response rate in the experimental arm.

With 95 PFS events, the study will have 80% power to detect a hazard ratio of 0.6 at an alpha level of 5% (1-sided).

The sample size and power calculations were performed in R (package “gsDesign”).

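### Does the 80% PFS power need an analysis trigger, or a second figure for the 10-JAN-2019 cutoff?

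*Protocol*

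**What the plan says.** Protocol section 10.9.1 gives one power figure for PFS: "With 95 PFS events, the study will have 80% power to detect a hazard ratio of 0.6 at an alpha level of 5% (1-sided"). The sSAP, section 3.9.1, has the same sentence: "With 95 PFS events, the study will have 80% power to detect a hazard ratio of 0.6".

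PFS is the second step of a fixed sequence (protocol 10.8, sSAP 3.8). It is tested only if ORR is significant at one-sided 5%. Nominal p-values are reported whatever the outcome of the sequence.

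The only prospective timing rule is in the sample-size row of protocol Table 9 and sSAP Table 1, where the ORR test is "based on all patients randomized with minimum 18 weeks of follow-up". Protocol 10.7.2 unblinds the study at the ORR database lock. The PFS methods (protocol 10.6.1.2, sSAP 3.6.1.2) set out censoring rules, a stratified log-rank test and a stratified Cox hazard ratio with its 95% CI, but no analysis date or event count.

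On calendar time, the synopsis says "The study is estimated to require approximately 3 years from the time the first participant signs the informed consent", and protocol 5.2 says "Enrollment was completed on 05-SEP-2018". The note opening protocol section 10 says "The final analysis of the study was conducted as described below, with a data cutoff of 10-JAN-2019" and then "As of Amendment 05, the study will therefore stop collecting efficacy data, including central review of imaging". Section 3.3 reports the outcome: "The results of the final efficacy analysis of this study indicated that the study did not meet the pre-specified endpoint".

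**The concern.** A log-rank test takes its power from the number of events, so a power figure for a given count means something in practice only if the analysis waits for that count. Here nothing makes it wait. The cutoff that was used follows the ORR follow-up rule, and Amendment 05 ended efficacy collection soon afterwards, so any shortfall below 95 events could not be made up. The 80% nevertheless remains the only PFS power in either document.

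The risk is one of interpretation. A nominal PFS p-value is reported although ORR failed. Someone who set a non-significant result beside the 80% could take it as stronger evidence against a hazard ratio of 0.6 than the events support.

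**Working it through.** **1. The plan's own figure.** Inputs from protocol 10.9.1 and 10.1: hazard ratio 0.6, one-sided alpha 5%, power 80%, 1:1 allocation. Schoenfeld's formula gives

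events = 4 × (1.645 + 0.842)² / (ln 0.6)² = 94.8, rounded up to 95.

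Power at E events is Φ(√E/2 × |ln 0.6| − 1.645). At E = 95 this is Φ(4.873 × 0.511 − 1.645) = 80.1%. The stated figure reproduces. It needs 95/148 = 64% of participants to have an event.

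**2. Which rule the cutoff follows.** From 05-SEP-2018 to 10-JAN-2019 is 127 days, or 127/7 = 18.1 weeks. Eighteen weeks after enrolment closed is 09-JAN-2019. The date therefore matches the ORR rule; no event target is documented for it.

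**3. Power against HR 0.6 at smaller counts (one-sided 5%).**

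| Events | 40 | 50 | 60 | 70 | 80 | 95 |
|---|---|---|---|---|---|---|
| Power | 48.8% | 56.4% | 63.1% | 68.9% | 73.9% | 80.1% |

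**4. Expected events at 10-JAN-2019.** The documents give no count, so this is a projection. Assumptions:

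- Exponential PFS and no drop-out.
- Control median 10.3 or 6.7 months: the observed median and lower 95% limit for pembrolizumab in the earlier phase 3 trial cited in protocol 3.1. Neither is a design input.
- Accrual ending 05-SEP-2018, starting either at the initial protocol date (06-JUN-2017) or on an assumed 15-JAN-2018.
- Accrual either uniform, or 58 then 90 participants. Protocol 5.2 expected about 90 more after Amendment 04, and 148 − 90 = 58. No date for Amendment 04 is shown, so the split dates are assumed.

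For a group accrued uniformly between a and b months before the cutoff, with λ = ln 2/median, the proportion with an event is 1 − [exp(−λa) − exp(−λb)] / [λ(b − a)]. The experimental arm uses HR × λ.

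Example: median 6.7 months, uniform accrual from 06-JUN-2017, HR 0.6. Then a = 4.17, b = 19.15 and λ = 0.1035. The proportions are 0.670 (control) and 0.498 (experimental), so events = 74 × 0.670 + 74 × 0.498 = 86.4.

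| Control median | Accrual | Events if HR 0.6 (power) | Events if HR 1.0 (power against 0.6) |
|---|---|---|---|
| 10.3 | from 15-JAN-2018, 58/90 split at 15-MAY-2018 | 48.1 (55%) | 57.9 (62%) |
| 10.3 | from 06-JUN-2017, split at 05-APR-2018 | 56.9 (61%) | 67.6 (68%) |
| 10.3 | uniform from 06-JUN-2017 | 65.9 (67%) | 77.6 (73%) |
| 6.7 | from 15-JAN-2018, split at 15-MAY-2018 | 66.4 (67%) | 78.4 (73%) |
| 6.7 | from 06-JUN-2017, split at 05-APR-2018 | 76.2 (72%) | 88.4 (78%) |
| 6.7 | uniform from 06-JUN-2017 | 86.4 (77%) | 99.1 (82%) |

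No HR 0.6 row reaches 95 events; one HR 1.0 row does. That row fits protocol 5.2 poorly: uniform accrual would put 148 × 303/456 = 98 participants in by 05-APR-2018, the date of version 03, against about 58 implied at the release of Amendment 04.

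**5. Was 95 a reasonable planning number?** With accrual from 03-NOV-2017, a split at 05-APR-2018 and HR 0.6, the model reaches 95 events about 5 months (median 6.7) to 12 months (median 10.3) after the cutoff. Both fall within about three years of the initial protocol, so the figure does not conflict with the planned duration.

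**6. What the planned estimate would show.** The 95% CI for the hazard ratio is the estimate divided and multiplied by exp(1.96 × 2/√E). For a hypothetical estimate of 1.0:

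- 58 events: 0.60 to 1.67
- 88 events: 0.66 to 1.52
- 95 events: 0.67 to 1.50

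The interval carries the event count with it.

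**The case for a change.** The strongest case for a change is that a fixed sequence should say when its second test takes place. The study is unblinded at the ORR database lock, so if ORR had succeeded, the date of the formal PFS test would still have been open once results were known. Amendment 05 then closed off the 95-event analysis without qualifying the 80%, and the nominal p-value is reported next to it. A short note would cost almost nothing.

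Part of this stands. No visible passage sets a PFS trigger, and at the cutoff the power was probably below 80%. But the open testing date mattered only if ORR was significant, and it was not. A note saying that the 80% applies at 95 events would repeat the opening words of the sentence it qualifies. The observed count, and the power at that count, are results; they do not belong in a planning section or in an sSAP written for Amendment 04. The study report is not among the documents, so nothing shows that the count is missing from it. Any PFS cutoff set in another document would also be out of view here.

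**Conclusion.** The concern is right on the facts but calls for no change to the plan. The 80% is correct (80.1% by Schoenfeld) and explicitly conditional on 95 events, and neither document claims it for the 18-week cutoff. The missing trigger is a gap in detail that no longer affects any decision: success rests on ORR alone, ORR failed, and the sequence stopped before PFS.

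The likely size is 48 to 86 events and 55% to 77% power at 10-JAN-2019 if the hazard ratio were 0.6. That rests on exponential PFS, no drop-out, control medians borrowed from another trial and assumed accrual. With no true effect, one pattern gives 99 events, so a shortfall is probable and not established.

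The remaining risk is that someone reads a nominal PFS result as coming from an 80%-powered comparison. The hazard ratio and 95% CI already planned guard against that, and normal reporting would put the event count beside them. The comparison should be called 80% powered only if 95 events had occurred. No result or conclusion would change by editing protocol 10.9.1 or sSAP 3.9.1.

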10.10 Subgroup Analyses

To determine whether the treatment effect is consistent across various subgroups, the between-group treatment effect for OS, PFS, and ORR (with a nominal 95% CI) will be estimated and plotted by treatment group within each category of the following classification variables:

- Stratification factor
 - Predominant tumor histology (squamous vs non-squamous)
- Geographic region (East Asia vs non-East Asia)
- ECOG performance status (0 vs 1)

- Age category (<65, ≥65 years)
- Sex (female, male)
- Race (white, non-white)
- Smoking status (never vs former/current smoker)
- Brain metastasis (presence vs absence)

[figure not shown]
10.11 Compliance (Medication Adherence)

Drug accountability data for study treatment will be collected during the study. Any deviation from protocol-directed administration will be reported.

10.12 Extent of Exposure

[figure not shown]
Extent of exposure for a participant is defined as number of cycles in which the participant receives the study medication. Summary statistics will be provided on extent of exposure for the APaT population.

11. References

[Addendum 1 to IB Edition 9 2017] EPACADOSTAT (INCB024360) – Investigators Brochure v9 Addendum 1, 03-Mar-2017. 04MX65

[Beatty, G. L., et al 2017] Beatty GL, O'Dwyer PJ, Clark J, Shi JG, Bowman KJ, Scherle PA, et al. First-in-Human Phase I Study of the Oral Inhibitor of Indoleamine 2,3-Dioxygenase-1 Epacadostat (INCB024360) in Patients with Advanced Solid Malignancies. Clin Cancer Res. 2017 Jan 4. [Epub ahead of print]. 04NM2W

[figure not shown]
[figure not shown]
[Boon, T. 1996]	Boon T, van der Bruggen P. Human tumor antigens recognized by T lymphocytes. J Exp Med. 1996 Mar 1;183(3):725-9.	049MF6
[Boyer, E. W. 2005]	Boyer EW, Shannon M. The Serotonin Syndrome. N Engl J Med 2005;352:1112-20	04FRYY
[Brandacher, G., et al 2006]	Brandacher G, Perathoner A, Ladurner R, Schneeberger S, Obrist P, Winkler C, et al. Prognostic value of indoleamine 2,3-dioxygenase expression in colorectal cancer: effect on tumor-infiltrating T cells. Clin Cancer Res. 2006 Feb 15;12(4):1144-51.	049MFB
[Disis, M. L. 2010]	Disis ML. Immune regulation of cancer. J Clin Oncol 2010;28(29):4531-8.	00VMNJ
[Ercolini, A. M., et al 2005]	Ercolini AM, Ladle BH, Manning EA, Pfannenstiel LW, Armstrong TD, Machiels JP, et al. Recruitment of latent pools of high-avidity CD8(+) T cells to the antitumor immune response. J Exp Med. 2005 May 16;201(10):1591-602.	049MFL
[Fallarino, F., et al 2006]	Fallarino F, Grohmann U, You S, McGrath BC, Cavener DR, Vacca C, et al. The combined effects of tryptophan starvation and tryptophan catabolites down-regulate T cell receptor zeta-chain and induce a regulatory phenotype in naive T cells. J Immunol. 2006 Jun 1;176(11):6752-61.	049PTL
[Frumento, G., et al 2002]	Frumento G, Rotondo R, Tonetti M, Damonte G, Benatti U, Ferrara GB. Tryptophan-derived catabolites are responsible for inhibition of T and natural killer cell proliferation induced by indoleamine 2,3-dioxygenase. J Exp Med. 2002 Aug 19;196(4):459-68.	049PSY

12.1 Appendix 1: Abbreviations and Trademarks

Abbreviation	Definition
1L	first-line (therapy)
AE	adverse event
AEOSI	adverse events of special interest
ALK	anaplastic lymphoma kinase
ALT	alanine aminotransferase
APaT	all participants as treated (population)
AST	aspartate aminotransferase
BCG	Bacillus Calmette-Guérin
BICR	blinded independent central review
BID	twice daily
C1D1	Cycle 1 Day 1
C2D1	Cycle 2 Day 1
CI	confidence interval
CNS	central nervous system
COPD	chronic obstructive pulmonary disease
CR	complete response
CRF	case report form
CSR	Clinical Study Report
CT	computed tomography
CTLA-4	cytotoxic T-lymphocyte-associated protein 4
DCR	disease control rate
DMC	Data Monitoring Committee
DOR	duration of response
ECG	electrocardiogram
ECI	event of clinical interest
ECOG	Eastern Cooperative Oncology Group
eCRF	electronic case report form
EGFR	epidermal growth factor receptor

Abbreviation	Definition
SAE	serious adverse event
SAP	Statistical Analysis Plan
SD	stable disease
SNRI	serotonin-norepinephrine reuptake inhibitor
SoA	Schedule of Activities
SOC	standard of care
SS	serotonin syndrome
sSAP	supplemental Statistical Analysis Plan
SSRI	selective serotonin reuptake inhibitor
TB	tuberculosis
TDLN	tumor draining lymph nodes
TPS	tumor proportion score
T-reg	regulatory T-cell
█	████████████████████
█	██
WOCBP	woman of child bearing potential

12.2 Appendix 2: Clinical Laboratory Tests

- The tests detailed in [Table 14](#) will be performed by the local laboratory.
- Protocol-specific requirements for inclusion or exclusion of participants are detailed in Section 6 of the protocol.
- Additional tests may be performed at any time during the study as determined necessary by the investigator or required by local regulations.

Table 14 Protocol-Required Safety Laboratory Assessments

Laboratory Assessments	Parameters			
Hematology	Platelet Count		RBC Indices:	WBC count with Differential: Neutrophils Lymphocytes Monocytes Eosinophils Basophils
	RBC Count		MCV	
	Hemoglobin		MCH	
	Hematocrit		%Reticulocytes	
	PT or INR aPTT or PTT ^a			
Chemistry	Blood Urea Nitrogen (BUN) or urea (one or the other should be collected per institutional standard; both tests are not required)	Potassium	Aspartate Aminotransferase (AST)/ Serum Glutamic-Oxaloacetic Transaminase (SGOT)	Total bilirubin (and direct bilirubin, if total bilirubin is elevated above the upper limit of normal)
	Albumin	A measure of carbon dioxide (CO ₂ or bicarbonate) ^b	Chloride	Phosphorous
	Creatinine	Sodium	Alanine Aminotransferase (ALT)/ Serum Glutamic-Pyruvic Transaminase (SGPT)	Total Protein
	Glucose [Indicate if fasting, or nonfasting]	Calcium	Alkaline phosphatase	Amylase
	Lipase			
Routine Urinalysis	
 • Specific gravity • Glucose, protein, blood, ketones by dipstick • Microscopic examination (if blood or protein is abnormal) • Pregnancy test, as needed for woman of childbearing potential (WOCBP) within 72hrs before first dose 			

Laboratory Assessments	Parameters
Other Tests (performed locally unless not feasible to perform at the site)	
 • Thyroid panel: TSH, FT4, FT3/T3 • Follicle-stimulating hormone (as needed in woman of non-childbearing potential only) • Serum β human chorionic gonadotropin (β-hCG) pregnancy test (as needed for WOCBP) • Serology: 
 ○ Hepatitis B surface antigen, HBV-DNA ○ HCV-RNA, HCV antibody (if HCV-RNA is not the local standard of care) ○ HIV-RNA (if required by local regulations)

Abbreviations: ALT = alanine aminotransferase; aPTT = activated partial thromboplastin time; AST = aspartate aminotransferase; BUN = blood urea nitrogen; DNA = deoxyribonucleic acid; FT4 = free thyroxine; HCV = Hepatitis C Virus; INR = international normalized ratio; MCH = mean corpuscular hemoglobin; MCV = mean corpuscular volume; PT = prothrombin time; PTT = partial thromboplastin time; RNA = ribonucleic acid; RBC = red blood cells; SGOT = serum glutamic oxaloacetic transaminase; SGPT = serum glutamic-pyruvic transaminase; SoC = Standard of Care; T3 = triiodothyronine; TSH = thyroid stimulating hormone (thyrotropin); WBC = white blood cells.
 
Notes:
 
 a. PTT may be performed if the local lab is unable to perform aPTT. b. If available as SoC in your region. The carbon dioxide may be either a measurement of CO₂ or bicarbonate as an electrolyte. 	

Investigators must document their review of each laboratory safety report.

